1.3.2 Rationale for Dose Selection

In the first in human study (Protocol number 001, refer to IB), which treated a variety of tumor types, pembrolizumab showed evidence of target engagement and objective evidence of tumor size reduction at all dose levels (1 mg/kg, 3 mg/kg and 10 mg/kg every 2 weeks). No DLT was observed and no MTD reached at these dose levels. Dose level 10 mg/kg every 3 weeks was evaluated in previously treated patients with NSCLC in Part C of Protocol 001. Pembrolizumab has also shown signs of efficacy and acceptable PK and PD results when administered both every 2 weeks and every 3 weeks. PK data analysis of pembrolizumab administered intravenously every 2 weeks showed slow systemic clearance, limited volume of distribution, and a long half-life (refer to IB).

Pharmacodynamic data (IL-2 release assay) suggested that peripheral target engagement is durable (>21 days). Previously treated patients with NSCLC in PN001 Part C have experienced durable objective responses with acceptable toxicity when treated with pembrolizumab at 10 mg/kg every 3 weeks. Preliminary data in patients with melanoma and NSCLC demonstrates objective responses by pembrolizumab when administered at the 2 mg/kg every 3 weeks dose and schedule. These results document efficacy results with both 2 mg/kg and 10 mg/kg doses. The additional dose level of 1 mg/kg was selected based on efficacy estimated by PK-PD modeling studies (discussed below) and concerns with safety given multiple intravesical administrations.

A syngeneic mouse tumor efficacy experiment, that included PK sampling and tissue receptor occupancy was conducted with a surrogate antibody and analyzed by translational PK-PD modeling. Results were extrapolated to man with inclusion of human relevant parameters for PK, pembrolizumab binding properties to PD-1 and the FcRN receptor, and

NU Study Number: NU 15U06
Merck Study Number: 3475-265

clinical NSCLC growth patterns, effectively normalizing dosing for humans in this model. This analysis led to the conclusion that the lowest dose of pembrolizumab with the potential to be equivalent to 10 mg/kg of pembrolizumab was 1-2 mg/kg. Considering the lack of clinical experience with intravesical administration of pembrolizumab and the need for multiple administrations, the dose 1 mg/kg was selected as the start dose in this study and will be used in first cohort of three evaluable subjects. Additional dose levels will include 2 mg/kg and 10mg/kg (see details of doses escalation on Section 4.3).

Because of uncertainty as to which dose schedule will have the better efficacy and safety profile in patients with BCG-refractory NMIBC, two dosing intervals of pembrolizumab will be utilized in this trial, every 2 weeks during induction therapy until week 17 (first cystoscopy) and every 6 weeks for the remaining period of maintenance phase (weeks 23, 29, 35, 41, 47). The shorter interval during induction therapy is based on the hypothesis that maximizing the PD-1 blockade during the BCG instillation might enhance the anti-tumor effect.

There is a possibility of adding an expansion cohort of up to 10 subjects to further define safety and efficacy of pembrolizumab. This will be determined by Merck after completion of the dose escalation phase.

1.3.3 Rationale for Exploratory Studies

Pembrolizumab has been shown to modulate the levels of several cytokines during studies using cultured blood cells from healthy donors, cancer patients, and primates (refer to IB). The correlative studies on this trial will explore humoral and cellular responses to pembrolizumab and BCG treatments by measuring cytokines (i.e., IL-2, IL-6, IL-8, IL-10, IL-18, IFN γ and TNF- α) in urine and serum samples and analyzing peripheral blood lymphocyte phenotypes.

Prior experiments with tumor response to BCG suggested that up-regulation of Th1 cytokines (i.e., IFN γ , IL-2, IL-12) is associated with BCG response and increased levels of Th2 cytokines (i.e., IL-6 and IL-10) correlate with recurrence ⁵³⁻⁵⁵. Induction of IL-2 mRNA in peripheral-blood mononuclear cells also predicted antitumor response during BCG treatment of non-muscle invasive bladder cancer. Urinary IL-2 measured 6 and 8 hrs after BCG administration correlated with higher risk of recurrence, whereas urinary IL-10 and IFN γ did not present significant correlation with BCG failure ⁵⁵. Therefore, correlative studies will evaluate the profile of cytokine production in urine and serum samples of patients receiving BCG and pembrolizumab and correlate with toxicity and risk of progression of non-muscle invasive bladder cancer. Peripheral blood lymphocyte phenotype determination by flow cytometry will also be performed to explore possible correlations with therapeutic benefit and/or toxicity.

Tumor specimens collected prior to study entry and those obtained during the study will be tested for the expression of PD-1, PD-L1, PD-L2 and profile of immune cell infiltration by immunohistochemistry. This analysis will evaluate the effect of treatment on tumor expression of these molecules and to explore possible correlations with toxicity and risk of recurrence. Clinical studies with anti-PD1 and anti-PD-L1 antibodies have suggested a correlation between clinical response and expression of PD-L1 in tumors ^{15,56}. QualTek has developed and validated a PD-L1 IHC assay using

NU Study Number: NU 15U06
Merck Study Number: 3475-265

Merck's proprietary 22C3 antibody. This assay has served as the prototype companion diagnostic assay and has been used by QualTek to test thousands of clinical samples, including those for prospective enrollment. The PD-L1 IHC assay has been validated and tested in over 20 different tumor indications in various clinical studies and on thousands of archived FFPE samples. Use of the assay has resulted in numerous recent abstracts (ASCO 2014, 2015) and has also been cited in the April NEJM publication in NSCLC. The exploratory testing in this study will be conducted using the same assay, with Merck's proprietary antibody, that was developed for MK3475 clinical trials, and analyzed by the same seasoned pathologists who have been reviewing PD-L1 expression for Merck clinical samples.

2 OBJECTIVES & ENDPOINTS

2.1 Primary Objective & Endpoint

The primary objective of this phase I dose-escalation study will be to determine the maximum tolerated dose (MTD) of the study drug (pembrolizumab) when administered intravesically in combination with BCG in patients with high risk or BCG-refractory non-muscle-invasive bladder cancer (up to the individual maximum tolerated dose of each drug alone). The MTD will be defined as the highest dose that causes dose limiting toxicities (DLTs) in <2 of 6 patients.

2.2 Secondary Objectives & Endpoints

Secondary objectives and endpoints will include the following:

2.2.1 To describe the DLTs of pembrolizumab in combination with BCG in this population. DLTs will be defined as described in Section 4.3.1 and the period for assessing DLTs will be during the 2 week pre-induction phase and the seven weeks of induction phase.

2.2.2 To assess the safety and tolerability of the combination of pembrolizumab and BCG in subjects with high risk or BCG-refractory non-muscle-invasive bladder cancer. The number, frequency, and severity of adverse events (as defined by the NCI Common Terminology Criteria for Adverse Events or CTCAE v 4.03) will be recorded.

2.3 Exploratory Objectives & Endpoints

2.3.1 To characterize the pharmacokinetics (PK) of pembrolizumab in both blood and urine when administered intravesically in combination with BCG. This will be done on the first 3 patients only to provide exploratory data. (A limited amount of plasma PK testing may be performed on additional patients as described below.*) PK will be evaluated by serial blood and urine sampling at specified time points before and after treatment (described in Section 5) during weeks -2 and 4 for determination of plasma and urine concentration-time profiles and PK parameters of pembrolizumab. Blood PKs will be performed by an outside vendor; urine will be collected and stored in the [name] Lab for later analysis.

*A portion of the blood specimens that have been collected for cytokine analysis (time-points week -2, week 0, and week 17) may be used in plasma PK assays, per Principal Investigator discretion.

2.3.2 To measure humoral and cellular responses to tumor antigens on serum and urine samples by measuring the levels of cytokines (i.e., IL-2, IL-6, IL-8, IL-10, IL-18, IFN γ and TNF- α) and peripheral blood lymphocyte phenotype throughout treatment. Urine and blood samples will be collected before and

after dosing throughout treatment (as described in the study schema). Cytokines will be measured using ELISA assays. Lymphocyte profiles will be analyzed using automated flow cytometric techniques.

- 2.3.3 To determine the response rate in terms of complete pathologic response in this population assessed when patient undergoes cystoscopies (weeks 17, 25, 33, 41, and 49 if applicable). Patients will be examined via bladder cystoscopy and may undergo biopsy for pathological confirmation if needed. Responses will be categorized as yes or no for bladder recurrence.
- 2.3.4 To document the progression rate associated with the combination of intravesical pembrolizumab and BCG in patients with high risk or BCG-refractory non-muscle-invasive bladder cancer. Tumor progression will be defined as positive transurethral resection and/or biopsy.
- 2.3.5 To evaluate the relationship between tumor biomarkers PD-L1, PD-L2, PD-1 as defined by immunohistochemistry (IHC) and adverse effects and recurrence rate. This evaluation will be performed on archived tissue samples obtained at baseline and on fresh tissue from any subsequent biopsies performed during cystoscopies scheduled for weeks 17, 25, 33, 41, and 49. Expression of PD-1, PD-L1, PD-L2 and immune cell infiltration by IHC will be assessed and results will be correlated with adverse effects and recurrence rate.
- 2.3.6 To evaluate changes in genetic data using targeted whole exome sequencing of DNA and RNA-sequencing from the tumors pre and post-treatment. This evaluation will be performed on archived tissue samples obtained at baseline and on fresh tissue or FFPE tissue samples from any subsequent biopsies performed during cystoscopies scheduled for weeks 17, 25, 33, 41, 49 and at progression.
- 2.3.7 To bank any leftover blood, urine, and tissue samples that remain after other studies are complete for future, unspecified use.
- 2.3.8 To document the progression free survival rate associated with the combination of intravesical pembrolizumab and BCG in patients with high risk or BCG-refractory non-muscle-invasive bladder cancer. Progression free survival will capture disease progression and all-cause death.
- 2.3.9 To document the overall survival rate associated with the combination of intravesical pembrolizumab and BCG in patients with high risk or BCG-refractory non-muscle-invasive bladder cancer. Overall survival will capture all-cause death.
- 2.3.10 To investigate immune markers associated with the combination of intravesical pembrolizumab and BCG in patients with high risk or BCG-refractory non-muscle-invasive bladder cancer. Immune marker data that are assessed as standard of care at any time during trial participation will be analyzed and correlated with trial therapy and response.

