3.1 Inclusion Criteria

3.1.1 Patients must have a histologically documented recurrence of non-muscle-invasive bladder carcinoma (T1HG, T1HG after reTUR or BCG refractory; if patient has received BCG they can be Ta, Tis, or T1)

Note: Gross disease is not allowed, however positive urine cytology and carcinoma in situ is permitted.

3.1.2 Patients must be BCG-unresponsive. A patient is BCG-unresponsive if they meet one or more of the following criteria:

- Patient has persistent or recurrent high-grade Ta/CIS/ urothelial carcinoma after completing therapy with at least induction BCG (≥ 5 doses) and first round maintenance or second induction BCG (≥ 2 doses). Patient has high grade T1 urothelial carcinoma after induction BCG (≥ 5 doses) only or after induction BCG (≥ 5 doses) and first round maintenance or second induction BCG (≥ 2 doses).
- Patient is disease-free at completion of BCG (i.e., complete response) but then experiences a high-grade recurrence before or at the 6 month follow-up cystoscopy.
- Recurrence after treatment with at least 3 doses of a BCG refractory agent (for example, though not limited to, gemcitabine, docetaxel, valrubicin or an interferon adenovirus).

3.1.3 Patients must have received one course of induction treatment with BCG (4-6 weekly doses), irrespective of the interval since last treatment. Patients are allowed to have received any number of prior chemotherapy instillations.

NOTE: Patients may have received prior intravesical interferon.

NU Study Number: NU 15U06
Merck Study Number: 3475-265

3.1.4 Patients must be age \geq 18 years.

3.1.5 All patients positive for invasion must have imaging (CT scan or MRI) documenting normal upper urinary tracts and absence of locally advanced bladder cancer within 60 days prior to study registration.

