5 STUDY PROCEDURES

Table 5: Study Procedures

Timeline	Baseline	Treatment Period			Off Treatment	
	Screening ²	Pre-induction Phase (Day -14)	Induction Phase (weeks 0 thru 5)	Maintenance Phase: (weeks 7 thru 53)	End of Treatment Visit ²⁰	Follow-up ²¹
Assessments/Procedures	X		X	X		
Informed Consent	X					
History	X					
Physical exam ¹	X		X	X	X	
Concomitant meds	X	X	X	X	X	
ECOG Status	X	X	X	X	X	
Adverse events ³	X	X	X	X		X
Cystoscopy ⁴	X			X ^{4, 5}		
Urine cytology ⁴	X			X ⁴		
Imaging studies ⁶	X					
CBC with diff ⁷	X	X	X ⁷	X ⁷		
Chemistry labs ⁸	X	X	X	X ⁸		
Coagulation labs ⁹	X					
Thyroid tests ¹⁰	X			X ¹⁰		
Urinalysis	X		X	X	X	
Pregnancy test ¹¹	X					
Urine creatinine ¹²		X	X	X		
Urine PK sample ¹³		X	X			
Serum PK sample ¹⁴		X	X			
Research blood sample ¹⁵		X ¹⁵	X ¹⁵	X ¹⁵		
Research urine sample ¹⁶		X ¹⁶	X ¹⁶	X ¹⁶		
Tissue for research ¹⁷	X			X		
Pembrolizumab ¹⁸		X	X	X		
BCG ¹⁹			X	X		
Survival/disease status						X

- Physical exam will include weight and vital signs (temperature, pulse, and blood pressure). Height will be measured at baseline only. A full physical exam should be performed at baseline; thereafter, a directed physical may be performed prior to each treatment administration.

2. Screening labs should be completed within 14 days prior to registration (except for pregnancy test). All other screening assessments should be performed with 28 days prior to registration unless otherwise noted. Screening and pre-induction procedures may be performed on the same day, if desired.
3. Baseline symptoms should be recorded at screening.
4. Cystoscopies will be performed at baseline and then to check for recurrence at weeks 17, 25, 33, 41, and 49; these may be performed more often if clinically indicated. A urine cytology will be performed at the same time as each cystoscopy.
5. Treatment of patients who undergo biopsy for pathogenic response at weeks 17, 25, 33, 41, and 49 may be held for the outcome at discretion of the treating surgeon.
6. Only required for patients who are positive for invasion. Baseline imaging will consist of CT or MRI. Studies showing normal upper tracts and absence of locally advanced bladder cancer required within 60 days before study registration. Follow-up imaging is not required but may be performed if clinically indicated.
7. CBC will be performed at baseline pre-dose at each treatment visit, within 48 hours if necessary. CBC may be performed more often if clinically indicated.

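### The single complete pathologic response rate in 2.3.3 pools clearance of existing disease with staying recurrence-free, and does not say how cytology counts

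*Combined protocol and SAP*

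**What the plan says.** Section 2.3.3 states the aim as "To determine the response rate in terms of complete pathologic response in this population assessed when patient undergoes cystoscopies", at weeks 17, 25, 33, 41 and 49. Patients are examined by cystoscopy and "may undergo biopsy for pathological confirmation if needed". The scoring rule is "Responses will be categorized as yes or no for bladder recurrence".

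Section 3.1.1 sets the disease state at entry. On stage, "if patient has received BCG they can be Ta, Tis, or T1". On residual disease, "Gross disease is not allowed, however positive urine cytology and carcinoma in situ is permitted".

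Table 5, footnote 4 adds: "A urine cytology will be performed at the same time as each cystoscopy". Section 4.7 makes the bladder wash for cytology part of the flexible cystoscopy. Neither the response definition (2.3.3) nor the progression definition (2.3.4 and 4.1) mentions cytology.

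Section 4.1 defines the response-evaluable set by doses received and available safety data, not by disease at baseline. Section 9 plans descriptive statistics for response and names no split by baseline disease.

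**The concern.** The entry criteria create two kinds of patient. A resected Ta or T1 patient without CIS and with negative cytology enters with no visible disease. For that patient, a result of no recurrence means the bladder has stayed clear. A patient with CIS or positive cytology enters with evidence of disease that can clear, and only there can the result describe a response. The plan gives both results one name and one denominator.

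The scale also fits the second group poorly. CIS that never clears is persistence, not recurrence, and a yes/no recurrence call has no stated place for it. The word pathologic is not secured either, because biopsy is optional. Positive cytology is an accepted entry state, yet the plan does not say how to score a patient whose bladder looks normal at week 17 while cytology is still positive.

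At stake is what the figure can support. A reader would take it as evidence of activity, although it can move with the mix of patients while the drug effect stays fixed. The marker objectives inherit the problem. Objective 2.3.10 correlates immune markers with response. Objective 2.3.5 correlates tumour markers with recurrence rate (the Study Summary says tumour response rate). A marker that merely tracks CIS status could appear to predict outcome.

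**Working it through.** **Plan's own figures.** The plan gives no target rate, precision or sample size for response. Its only operating characteristic is the chance of escalating under the 3+3 rule, (1−p)³ + 3p(1−p)²·(1−p)³. This gives 90.6%, 49.4% and 17.2% at p = 10%, 30% and 50%, matching the stated 91%, 49% and 17%. It has no bearing on response.

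**Inputs for the pooled rate.** None is in the documents, so all three are assumptions:
- f: share entering with CIS and/or positive cytology
- C: their true complete response rate
- P: recurrence-free proportion in patients entering with neither

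**Formula.** Pooled rate = f·C + (1−f)·P. Moving f from 25% to 75% changes it by 0.5·(C−P).

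| C | P | f = 25% | f = 75% | Shift in points |
|---|---|---|---|---|
| 60% | 60% | 60% | 60% | 0 |
| 40% | 60% | 55% | 45% | 10 |
| 30% | 60% | 52.5% | 37.5% | 15 |
| 20% | 60% | 50% | 30% | 20 |
| 30% | 70% | 60% | 40% | 20 |

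The shift is half the gap between the two rates. It is zero when they are equal and 20 points when they differ by 40. A wider gap gives more: at C = 20%, P = 80% the pooled rate goes from 65% to 35%, which is 30 points.

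**Limiting case.** With C = 0 and P = 60% the pooled rate is 0.75 × 60% = 45% at f = 25%, 30% at f = 50% and 15% at f = 75%. A complete response rate well above zero would be reported although nobody with disease to clear had cleared it.

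**Sensitivity to a real effect.** A true 20-point gain confined to patients with disease at entry moves the pooled rate by f × 20, that is 5, 10 or 15 points at f = 25%, 50% or 75%.

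**Cytology.** Suppose a pooled rate of 60% from cystoscopy, and that 5%, 10% or 20% of the cystoscopy-negative patients have positive cytology. Counting them as failures gives 60% × 0.95 = 57%, 60% × 0.90 = 54% or 60% × 0.80 = 48%. One such patient is worth 1/24 = 4.2 points on the 24 of Sections 3 and 9, or 1/18 = 5.6 points on the 18 of Section 4.1. Those counts are ceilings, because Section 4.1 sets dosing requirements for the response set.

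**Precision.** Exact (Clopper-Pearson) 95% intervals are 29–71% for 12/24 and 21–79% for 6/12, the latter after an even split.

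**The case against.** The strongest reply is that this is an exploratory, descriptive endpoint in a dose-finding study. No hypothesis rests on it and no comparison of response between dose cohorts is planned. Descriptive statistics do not prevent a table by baseline stage, and splitting a small sample makes intervals that are already wide wider still. All of this stands, and it sets the weight of the point. It does not make the single figure interpretable, and the plan does not commit to such a table.

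Four stronger readings are tempting, and the documents do not support them.

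- *The rate mostly reflects case mix.* With no CIS share or subgroup rates given, this cannot be shown. The shift is zero if the two rates are equal.
- *The endpoint does not measure response at all.* In patients who enter with CIS, clearance does measure response. Nor does the absence of gross disease prove the others are tumour-free: Section 1.3.1 allows for residual tumour cells in the bladder wall.
- *Cytology is ignored and cytology-positive patients will be scored as responders.* The plan is silent, not prohibitive. A positive cytology could prompt the optional biopsy, so its role is unspecified.
- *This is the trial's only activity measure.* Progression rate, PFS and OS are also planned. Moreover, 2.3.5 as written in Section 2.3 uses recurrence rate, which a yes/no recurrence call does measure.

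**Conclusion.** The point holds as a cheap improvement to an exploratory endpoint. As defined, the 2.3.3 rate combines two quantities, depends on the share of patients entering with disease, and cannot be read as a complete pathologic response rate. How positive cytology with a negative cystoscopy is counted is left open.

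The size is unknown. The range of 0 to 20 points rests on assumed rates (equal; 20% against 60%; 30% against 70%) and on an assumed change in the share with disease at entry from 25% to 75%. It illustrates the dependence and does not estimate the bias in this trial. The structural point needs none of these assumptions, because it follows from reading 2.3.3, 3.1.1, 4.1 and 9 together. MTD determination, dose escalation and sample size are untouched.

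**What to change.** In 2.3.3 and Section 9:

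1. Report complete response only in patients with CIS and/or positive cytology at entry, showing CIS and cytology-only patients separately. In resected Ta/T1 patients with neither, report the recurrence-free proportion at the same visits. Give no pooled response rate.
2. For the analysis, count a complete response as negative cystoscopy and negative cytology, or a negative biopsy where one was taken for an abnormal result. Do not count positive cytology without a negative biopsy as a complete response. This classifies data already collected and requires no additional biopsies.
3. Report each proportion by visit with exact confidence intervals on the response-evaluable set of Section 4.1. Reconcile that section's maximum of 18 evaluable subjects with the 24 in Sections 3 and 9.
4. Use the same split when markers are correlated with response or recurrence (2.3.5, 2.3.10).

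The cost is mainly wording. The pathology report is already submitted at registration (Section 10.3), and cytology is already scheduled at baseline and at each cystoscopy. The price is smaller denominators and wider intervals, as in the 6/12 against 12/24 example, in return for proportions that each have a clear meaning.
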